6. SPECIFIC AIMS

Aim 1. To establish in AN feasibility and acceptability of a study design to understand the contributions of the selective DA D2 receptor agonist bromocriptine on PE and reversal learning.

Hypothesis 1.a. The DA D2 receptor agonist bromocriptine (1.25mg) will enhance fMRI PE response during a taste-reward PE paradigm in AN in ventral striatum and insula compared to placebo.

Hypothesis 1.b. The DA D2 receptor agonist bromocriptine (1.25mg) will enhance reversal learning and striatum brain response in AN during a monetary reversal learning task compared to placebo during fMRI.

Aim 2. To establish in AN feasibility and acceptability of a study design to understand the contributions of the selective DA D2/D3 receptor antagonist amisulpride on PE and reversal learning.

Hypothesis 1.a. The DA D2 receptor antagonist amisulpride (400mg) will reduce fMRI PE response in the insula and ventral striatum compared to placebo.

Hypothesis 1.b. The DA D2 receptor antagonist amisulpride (400mg) will reduce reversal learning and striatum brain response in AN during a monetary reversal learning task compared to placebo during fMRI.

Aim 3. To gather pilot data how fMRI brain response to the DA D2 receptor agonist bromocriptine or antagonist amisulpride differs between individuals with AN and healthy control women.

Hypothesis 3. We expect we will find an indication that bromocriptine will enhance PE (ventral striatum and insula) and reversal learning (frontal cortex) in AN more compared to the control group, while amisulpride causes the opposite.

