Each subject will complete three MRI scan days (Study Visit 1, Study Visit 2, and Study Visit 3). On each day, the subject will consume one of the three medications (amisulpride, bromocriptine or placebo). Each subject will complete a baseline scan (P-fMRI), Amisulpride scan (A-fMRI), and Bromocriptine scan (B-fMRI) spaced 3 days apart (2 to 4 day acceptable range). This randomized study has 6 medication study arms listed below:

On the morning of each study day, the PI or other study staff not running the fMRI scanning procedures will provide the study subjects the medication as per randomization. Other study personnel that will run the fMRI scanning procedures will be kept blinded from the applied medication. This will help reduce bias by the study personnel.

There are no rater applied assessments on the study days so there is no rater bias based on the personnel end. The fMRI data are objective and thus unbiased.

The investigator will not supply the investigational drug to any person not authorized under this part to receive it. (§312.61 Control of the investigational drug.)

Neither study drug is a controlled substance. Nevertheless, the study medication packages with the investigational drugs will be in a securely locked, substantially constructed cabinet, in the PI’s office, which is within an office suite that is locked and accessible only to the research personnel.

Should the subject have a serious adverse reaction that required emergency treatment, the PI would be contacted and the blinding of the medication order would be broken in order to allow adequate treatment of the patient by emergency department staff.

Each subject will be randomized to one of the following groups:

1.

Scan 1: P-fMRI
Scan 2: A-fMRI
Scan 3: B-fMRI

2.

Scan 1: P-fMRI
Scan 2: B-fMRI
Scan 3: A-fMRI

3.

Scan 1: A-fMRI
Scan 2: P-fMRI
Scan 3: B-fMRI

4.

Scan 1: A-fMRI
Scan 2: B-fMRI
Scan 3: P-fMRI

5.

Scan 1: B-fMRI
Scan 2: P-fMRI
Scan 3: A-fMRI

6.

Scan 1: B-fMRI
Scan 2: A-fMRI
Scan 3: P-fMRI

Medication dosage

Amisulpride – Single Dose 400 mg and scan 3 hours post ingestion

Bromocriptine – Single Dose 1.25 mg and scan 3 hours post ingestion

Amisulpride

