All paper data will be stored in locked cabinets in the PI office space at UC San Diego Health Eating Disorders Center for Treatment and Research ([name]). All electronic data will be stored on the VRD server created for [name] lab by the ACTRI (see section 16 PRIVACY AND CONFIDENTIALITY CONSIDERATIONS INCLUDING DATA ACCESS AND MANAGEMENT below for more details).

We will extract for both tasks mean parameter estimates from 18 predefined anatomical regions of interest (ROIs) (<http://marsbar.sourceforge.net/>), automated anatomical labeling Atlas, AAL (Tzourio-Mazoyer et al., 2002) based on previous studies (DeGuzman et al., 2017): dorsal and ventral anterior insula, caudate head, gyrus rectus, medial, middle and inferior OFC, ventral striatum (O'Doherty et al., 2004) and nucleus accumbens (Breiter et al., 1997). Extracted ROI data will be analyzed using SPSS 24 (IBM statistical software) using repeated measures ANCOVA. Extracted regional brain activation parameter estimates will be tested for normality with the Shapiro-Wilk test, rank-transformed when non-normally distributed and analyzed using repeated measures ANCOVA with covariates as in previous studies to account for confounding factors such as comorbidity or medication (DeGuzman et al., 2017). Spearman's rank will be used for correlation analyses and controlled for multiple comparisons using bootstrapping (1000 samples) (Westfall, 2011). We will also conduct exploratory whole-brain analyses to test for areas of interest outside of our predefined ROIs and create PE response maps, with maps thresholded at voxel level $p < 0.05$, FWE corrected (very stringent), 10 voxel minimum cluster contiguity, as well as voxel level $p < 0.001$ and $p < 0.05$ cluster level corrected (exploratory),

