Statistical Power. This is a developmental grant application and we cannot be certain whether the study has sufficient power. However, previous studies using comparable designs and similar sample sizes showed significant within and between group results (Diederer et al., 2017). Studies from our group (Frank et al., 2018a) indicated that subject groups of 20 per group should provide sufficient power based on for instance caudate nucleus PE parameter estimate means of 67.8 (adolescent AN) and 40.2 (adolescent controls), with a mean standard deviation of 28, to reach a power of 0.8, $p<0.05$. Thus, our sample size for the fMRI study should be adequate and be able to replicate our previous results (elevated PE) and provide adequate pilot data for the new analyses in this application. A main goal of this application to investigated data distribution, standard deviation, etc. for future studies.

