10. HUMAN SUBJECTS

Total Enrollment: 104 subjects (34 anorexia nervosa and 70 healthy controls)

Age Range: 18 to 29 years old

Gender: Female

Ethnic Background: All races and ethnicities

Health Status: See below

Description of Population to be Enrolled:

Subject population: Subjects will consist of female adults, ages 18 to 29 years old. We plan on completing a total of 44 subjects over 2-3 years. We expect to enroll up to an additional 60 subjects who will be disqualified during the screening process. Subjects will reflect the racial/ethnic composition of women in San Diego, CA. Total number of participants to be enrolled is 104.

Inclusion Criteria:

Healthy Controls

- Females ages 18-29 years
- Healthy body weight between 90 and 110 % average body weight since puberty.
- Regular monthly menstrual cycle
- Edinburgh Handedness Inventory Revised (EHI-R) LQ* score $> +200$
- English is primary language spoken

Anorexia Nervosa

- Females ages 18-29 years
- Diagnostic criteria. Current diagnosis of AN, including being underweight below 17.5 body mass index (BMI, kg/m^2), will have a severe fear of weight gain, body image distortion and absence of the menstrual cycle over three consecutive months.
- Edinburgh Handedness Inventory Revised (EHI-R) LQ* score $> +200$
- English is primary language spoken

Exclusion Criteria:

Healthy Controls

- Current pregnancy or breast feeding within last 3 months
- Illiterate/Blind individuals
- First degree relative with current or past eating disorder
- Current Medications other than BCP or IUD
- Contraindications to amisulpride or bromocriptine (as determined through medical history in bioscreen and PI interview) including: Syncopal migraine; Uncontrolled hypertension; Pheochromocytoma; Prolactinoma; Breast cancer; hypersensitivity/allergy to amisulpride or bromocriptine; History of long QT syndrome; Family history of sudden death or long QT syndrome; History of seizures or seizure disorder
- Past or present Axis I psychiatric disorder including substance or alcohol use disorder as determined through SCID-5 clinical interview
- Major Medical illness (as determined through medical history in bioscreen and PI interview) such as:
 - Conditions that are life threatening:
 - cancer
 - heart disease
 - stroke
 - HIV/AIDS
 - Conditions that are life threatening Conditions that cause serious disability without necessarily being life threatening:
 - stroke
 - closed head or spinal cord injuries
 - mental retardation

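### Between-woman covariates in the repeated measures ANCOVA are not needed for the within-AN drug contrasts of Aims 1 and 2 and, if entered uncentred with drug-by-covariate terms, would change what those contrasts estimate and cost power

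*Combined protocol and SAP*

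**What the plan says.** Section 9, Data Storage and Data Analysis Plan, covers both tasks with one method: "Extracted ROI data will be analyzed using SPSS 24 (IBM statistical software) using repeated measures ANCOVA". It adds that the estimates will be "analyzed using repeated measures ANCOVA with covariates as in previous studies to account for confounding factors such as comorbidity or medication".

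The plan does not give a final covariate list, the coding, or whether covariates are centred. It also does not say whether drug-by-covariate terms are in the model, whether Aims 1 and 2 are tested in AN women alone or jointly with controls, or which output (a within-subject F test or a contrast of adjusted means) decides a hypothesis.

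Section 6 states the hypotheses as drug against placebo. Under Aim 1, bromocriptine "will enhance fMRI PE response during a taste-reward PE paradigm in AN in ventral striatum and insula compared to placebo". Under Aim 2, which is also set in AN, amisulpride "will reduce fMRI PE response in the insula and ventral striatum compared to placebo". Section 9 gives every woman amisulpride, bromocriptine and placebo on separate scan days, with 2 to 4 days between scans accepted.

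**The concern.** Adjusting for comorbidity or medication makes sense when AN women are compared with controls. A drug-placebo difference within one woman is another matter. Anything constant across her three scans is the same on both sides of the subtraction, so it cannot confound the difference. The reason the plan gives for the covariates therefore does not apply to Aims 1 and 2.

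The covariates may also do harm there. In a repeated measures model with drug-by-covariate terms, the drug main effect is the intercept of the within-woman contrast regressed on the covariates, so it is the drug effect at covariate value zero. With raw 0/1 coding, zero means no comorbidity and no medication. The test then describes a subgroup of the AN women, with a larger standard error, and a real average drug effect could be reported as absent. The plan also wants this pilot to inform the distributions and standard deviations used in later studies, so an effect estimated at an unstated covariate value would carry forward.

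**Working it through.** **The plan's own figure.** Section 9, Statistical Power, says that "subject groups of 20 per group should provide sufficient power", from "caudate nucleus PE parameter estimate means of 67.8 (adolescent AN) and 40.2 (adolescent controls), with a mean standard deviation of 28". The standardised difference is (67.8 − 40.2)/28 = 27.6/28 = 0.986. A two-sided 0.05 t test reaches power 0.82 with 18 per group and 0.86 with 20. The figure reproduces and is slightly conservative. It is a between-group calculation, so it neither supports nor is affected by the within-AN point below.

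**Inputs for the within-AN test**
- AN completers: 22. Section 10 says "We plan on completing a total of 44 subjects over 2-3 years" and gives no split by group; equal halves are an assumption.
- Drug-placebo effect: 0.6 SD of the paired difference (assumed), with 1.0 SD as a second value.
- Covariates: one, or two independent, coded 0/1, at assumed prevalences of 30, 50 and 70%.
- Two-sided 0.05. The plan does not state sidedness.

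**Model.** For woman *i*, let D = drug minus placebo response, and D = b0 + b1·x + error, with error variance σ². A covariate without a drug-by-covariate term cancels in D and does nothing. With the term, the drug main effect is b0, and

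Var(b0) = (σ²/n) × V, where
- V = 1 if covariates are mean-centred;
- V = 1 + p²/[p(1 − p)] = 1/(1 − p) for one raw 0/1 covariate with prevalence p;
- V = 1 + 2p/(1 − p) for two independent ones.

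The one-covariate case can be checked directly. The intercept is the mean of D among the n(1 − p) women at zero, which is 22 × 0.5 = 11 women at 50%.

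**Power.** Noncentral t, noncentrality 0.6 × √(22/V), df = 22 − 1 − k for k covariates. With no covariate the noncentrality is 0.6 × √22 = 2.81 and power is 0.77. With one or two centred covariates it is 0.76.

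| Raw 0/1 covariates | Prevalence | V | SE factor √V | Power |
|---|---|---|---|---|
| One | 30% | 1.43 | 1.20 | 0.61 |
| One | 50% | 2.00 | 1.41 | 0.47 |
| One | 70% | 3.33 | 1.83 | 0.31 |
| Two | 30% | 1.86 | 1.36 | 0.50 |
| Two | 50% | 3.00 | 1.73 | 0.34 |
| Two | 70% | 5.67 | 2.38 | 0.20 |

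**Sensitivity to effect size.** At 1.0 SD, power is 0.99 with no covariate and 0.88 with one raw covariate at 50%.

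**Check on the three-condition F test.** A simulation with 20 AN women and an effect set for about 80% power gave 0.79 with no covariate, 0.49 with one raw covariate at 50%, and 0.79 with it centred.

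**Joint AN-control model.** Section 10 excludes controls for any Axis I disorder and for current medication other than contraceptives, so both covariates are zero in every control. With 22 per group and 50% prevalence in AN, the overall mean is 25%. An AN drug effect evaluated there has SE factor √(1 + 0.25²/0.25) = 1.12 and still does not describe AN as enrolled. Centring must therefore be at the AN mean.

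**The case against.** A reader might infer that the plan as written makes the drug test a test at covariate zero and removes most of its power. The documents do not support either statement.

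- The plan does not say that covariates are uncentred or that drug-by-covariate terms are kept, and it refers covariate handling to previous studies. What the software does by default is not in the documents.
- The hypotheses are pairwise contrasts, and nothing says that an omnibus F test decides them. A contrast of adjusted means at the AN covariate mean does not have this problem.
- Losing more than half the power needs particular conditions. With 20 AN women and 80% power at the start, one 0/1 covariate must exceed about 63% prevalence, or two must each exceed about 45%. Other codings or a raw continuous score would do more damage, but the plan names none.
- Unequal drug effects can favour either analysis. Take a 1.0 SD effect confined to one subgroup, 22 women and 60% medicated. If only medicated women respond, power is 0.05 raw against 0.74 centred. If only unmedicated women respond, it is 0.78 raw against 0.44 centred.

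Two further objections carry less weight. AN women are scanned within 1 to 2 weeks of admission while treatment continues, so medication could change between scans. The documents do not say that it does, and a single covariate value per woman would not capture such a change. Aims 1 and 2 are also framed as feasibility and acceptability, and the plan admits that power is uncertain. That lowers the stakes, but the directional drug hypotheses remain.

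**Conclusion.** The point holds in conditional form. The only stated region-of-interest model for Aims 1 and 2 carries between-woman covariates that those contrasts do not need for confounding control, and nothing in the plan prevents them from shifting the drug test to women with neither comorbidity nor medication. If they enter raw with drug-by-covariate terms, power falls from 0.77 to between 0.61 and 0.20 across the scenarios shown. It stays at 0.76 with centring.

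These sizes rest on 22 AN completers, a 0.6 SD effect, independent 0/1 covariates and assumed prevalences, none of which the documents give. At 1.0 SD the loss is smaller. The change in what is estimated does not depend on the effect size: under the same conditions, the reported effect is not the effect in AN as enrolled unless the drug effect is unrelated to the covariates. The plan's 20 per group and the use of covariates in the AN-control comparison are not in question here.

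**What to change.** Add to Section 9, Data Storage and Data Analysis Plan:

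> The drug-placebo contrasts within AN (Aims 1 and 2) are tested in AN women without between-woman covariates. Any covariate kept in a repeated measures model is mean-centred. When the AN drug effect is estimated, centring is within AN, because controls are zero on comorbidity and medication by exclusion. Drug-by-covariate terms are reported separately as exploratory.

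This costs the added text and one recoding step, with no new data and no burden on participants. The no-covariate test gives up a little precision if a covariate strongly modifies the drug effect. In the two subgroup examples above, its power is about 0.67 against 0.74 centred, and about 0.36 against 0.44 centred.

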 - congenital malformations.
 - Conditions that cause significant pain or discomfort that can cause serious interruptions to life activities:
 - severe allergies
 - migraine
 - arthritis
 - sickle cell disease
 - Conditions that require major commitments of time and effort from care-givers for a substantial period of time:
 - mobility disorders
 - blindness
 - Alzheimer's disease and other dementias
 - chronic obstructive pulmonary disease
 - paraplegia or quadriplegia
 - Down's syndrome
 - depression
 - Conditions that may require frequent monitoring:
 - diabetes
 - conditions requiring anticoagulation treatment
 - severe asthma
 - severe allergies
 - schizophrenia and other psychotic illnesses.
 - Conditions that predict or are associated with severe consequences:
 - hypertension (associated with heart disease)
 - depression (associated with suicide)
 - diabetes (associated with blindness, kidney failure)

- alcohol and other substance abuse (associated with intentional and unintentional injuries).
- Recent history of suspected substance abuse or a lifetime history of psychostimulant abuse and/or dependence
- Metal implants or braces (as determined through fMRI screening form)

Anorexia Nervosa

- Pregnancy or breast feeding within last 3 months
- Lifetime history of bipolar disorder or psychosis
- Illiterate/Blind individuals
- Contraindications to amisulpride or bromocriptine (as determined through medical history in bioscreen and PI interview) including: Syncopal migraine; Uncontrolled hypertension; Pheochromocytoma; Prolactinoma; Breast cancer; hypersensitivity/allergy to amisulpride or bromocriptine; History of long QT syndrome; Family history of sudden death or long QT syndrome; History of seizures or seizure disorder
- Use of an anti-psychotic or other dopamine acting medication including stimulants within the past week at time of MRI
- Recent history of substance abuse or dependence (within the last month)
- Major Medical illness (as determined through medical history in bioscreen and PI interview) such as:
 - Conditions that are life threatening:
 - cancer
 - heart disease
 - stroke
 - HIV/AIDS
 - Conditions that are life threatening Conditions that cause serious disability without necessarily being life threatening:
 - stroke
 - closed head or spinal cord injuries
 - mental retardation
 - congenital malformations.
 - Conditions that cause significant pain or discomfort that can cause serious interruptions to life activities:

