14. POTENTIAL RISKS

Potential Risks

It is our experience that individuals with eating disorders including AN are willing to cooperate with such studies. Over the past 12 years we have recruited and studied close to 400 subjects and had no incident that would indicate any risk. The studies were not psychologically traumatic to adolescents or adults in the past. We do not feel that these studies pose any significant psychological risk for patients or control study subjects. Many measures are in place to assess and avoid risks.

Computer Testing/Interviewing. The main risks associated with these procedures are fatigue and irritability with the testing procedure. The investigator and research associates are trained to frequently ask the subjects about their willingness and ability to continue with testing. If a subject expresses concerns about continuing with testing, the investigator has instructed the research associate to stop testing, offer a break, or, if the subject is not willing to continue, to terminate the testing session. Overall, however, previous studies have not resulted in any significant discomfort or anxiety expressed by the participating subjects.

Social Risk. There is no social risk associated with the participation in this study, all results will be kept strictly confidential and will not be used to influence any clinical decision making. There are no legal risks associated with these paradigms. There are no other known risks associated with participation in this study. AN patients will continue to receive their current treatment, which is not being suspended or modified in any way for research purposes.

fMRI Brain Imaging. There are two major sources of risk. First, there could be risk from the magnetic field in the MR scanner, second the subject may experience discomfort being in the confined environment of the scanner (claustrophobia) with exposure to noise, and third, the subject may experience discomfort carrying out the task. The Sharp & Children's MRI Center is run by full time trained technicians who have extensive experience and training to conduct safely the here proposed studies. In addition all research personnel involved in this study is/will be trained in MR safety by the imaging center staff.

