16. PRIVACY AND CONFIDENTIALITY CONSIDERATIONS INCLUDING DATA ACCESS AND MANAGEMENT

Privacy and Confidentiality

Setting. All consenting procedures will be conducted in the private offices of the PI and research staff at the UC San Diego Health Eating Disorders Center for Treatment and Research. The Pre-Scan Study Visit will take place at ACTRI (primary option) or at San Diego Medical Care or LabCorp facilities (secondary option). Study Visit 1, Study Visit 2, and Study Visit 3 procedures will be conducted at the Sharp and Children's MRI Center.

Safeguards to Protect Subject Confidentiality. Sensitive information about a subject's medical and psychiatric history including substance abuse and treatment histories are collected as part of this research study. To protect the privacy we will keep all subject folders in locked file cabinets in the locked offices of the PI and research coordinator. Only the PI and research staff will have access to these files. In addition, the possible risk of loss of confidentiality is explained to the subject as a possible risk and he/she has the option of not participating in the study. Information about current psychiatric illness and current medication use is collected as research data. In addition, information about drug abuse and dependence is collected as part of the study. The patient populations included in this research study include participants who have been diagnosed with a medical or psychiatric condition. While this information is considered sensitive, it is necessary to collect this data to provide an accurate description of our subject populations and use as a comparison to our healthy control populations. All subjects are told in the consenting process that they can choose to not answer any question. While they do have the right to refuse to have this sensitive data collected, some of the sensitive data are necessary to collect for the outcome of the study (including substance use, medical conditions, etc.), therefore, the principal investigator may choose to withdraw or not include any participant who chooses to not have this sensitive data collected.

Data Storage and Access

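### The three-visit crossover analysis names no visit term, and comorbidity and medication covariates, if binary and crossed with drug, would change what Aim 3's group x drug test estimates

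*Combined protocol and SAP*

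**What the plan says.** Section 9 (Overview of Study Procedures; Handling of Study Medication) sets out a three-period crossover. There are three scans about 3 days apart, one per treatment, with each subject randomised to one of the six possible orders. Both tasks are repeated at each scan.

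Section 9 (Data Storage and Data Analysis Plan) analyses the regional estimates in SPSS by "repeated measures ANCOVA with covariates as in previous studies to account for confounding factors such as comorbidity or medication", citing an earlier study for the covariates. It gives no coding for them, does not say which tests take them, and mentions no visit, period or order effect.

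Aim 3 in section 6 compares drug response between groups. Hypothesis 3 expects bromocriptine to enhance the responses "in AN more compared to the control group, while amisulpride causes the opposite".

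Section 10 excludes controls for "Past or present Axis I psychiatric disorder including substance or alcohol use disorder as determined through SCID-5 clinical interview" and for "Current Medications other than BCP or IUD". Depression also appears among the controls' medical exclusions ("depression (associated with suicide") but not in the matching AN list. For AN, the medication exclusion is narrower: "Use of an anti-psychotic or other dopamine acting medication including stimulants within the past week at time of MRI". Section 14 adds that "AN patients will continue to receive their current treatment, which is not being suspended or modified in any way for research purposes", and section 16 that "Information about current psychiatric illness and current medication use is collected as research data".

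**The concern.** **Visit.** Before the third scan each subject has had 2 x 280 = 560 taste trials and, by the stated block structure, 2 visits x 3 blocks x 9 = 54 reversals. If responses drift with practice or habituation, a model without visit leaves the drift in the error term. Power for the drug contrasts falls, and the residual SD mixes trend with noise. Section 9 (Statistical Power) names the standard deviation among the things the study is meant to learn for later work.

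**Covariates.** An indicator for a psychiatric diagnosis or a psychotropic drug is zero in every control by eligibility and can vary only within AN. Its slope is therefore estimated from AN alone. If that slope is allowed to differ by drug, the adjusted group x drug estimate refers to AN women without the attribute, whereas Hypothesis 3 is about AN. That can be a legitimate target, but the plan does not name it. A result reported simply as AN versus controls would describe a subset.

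**Working it through.** **The plan's own figure.** Section 9 (Statistical Power) gives 20 per group from means of 67.8 and 40.2 and SD 28. The standardised difference is 27.6/28 = 0.986. A two-sided two-sample t-test at 0.05 needs 18 per group for power 0.80, and 20 per group gives 0.86, so the figure holds. It concerns an unadjusted AN-versus-control difference. The documents give no inputs for a drug contrast, a visit trend or covariate prevalence, so those below are assumptions.

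**Visit term.** Let the residual SD be 1 and the gains at visits 2 and 3 be a and b. Over six equally likely orders, the trend contribution to a drug-placebo difference has mean zero, hence no bias. Its mean square is (a² + b² + (b−a)²)/3. Without the trend the difference has variance 2, so the variance factor is

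f = 1 + (a² + b² + (b−a)²)/6.

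Take n = 22 AN (44 planned completers, equal split assumed) and a drug effect of 0.88, chosen to give power near 0.80. The noncentrality is 0.88/√(2f/22). The subject + drug model has 66 − 22 − 2 = 42 df.

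| Gains a/b | f | Power without visit | With visit |
|---|---|---|---|
| 0/0 | 1.00 | 0.81 | about 0.80 |
| 0.25/0.5 | 1.06 | 0.79 | about 0.80 |
| 0.5/1.0 | 1.25 | 0.72 | about 0.79 |
| 1.0/1.5 | 1.58 | 0.62 | about 0.79 |

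The last column is simulated. Simulated power without the term agrees with the table to within about one point. A paired t-test on difference scores, with 21 df, is about two points lower (0.79, 0.77, 0.70, 0.60). Simulated type I error was 0.04 to 0.06 throughout.

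**Covariate.** Regress the drug-placebo difference on group and a binary covariate that is zero in all controls, with share p in AN. The group coefficient equals controls versus AN with covariate zero. In one simulated data set (20 per group, 12 of 20 AN medicated) the adjusted coefficient was 0.599, identical to controls versus unmedicated AN. The contrast with all AN was −0.049.

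This regression is the crossed model. In a long-format check, adding the covariate as a main effect only left the group x bromocriptine estimate at 0.0544. Crossing it with drug moved the estimate to 0.2385.

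Relative to 2/n, the variance factor with one covariate is [1/(1−p) + 1]/2 = 1 + p/(2(1−p)). With two independent covariates of equal prevalence it is 1 + p/(1−p). Take n = 20 per group, an effect of 0.909 SD (unadjusted power 0.80), the same response in all AN, and covariates that explain nothing:

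| Assumed p | One covariate: factor, power | Two covariates: factor, power |
|---|---|---|
| 20% | 1.13, 0.75 | 1.25, 0.71 |
| 30% | 1.21, 0.72 | 1.43, 0.65 |
| 50% | 1.50, 0.63 | 2.00, 0.51 |

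If AN subgroups respond differently, the estimate also shifts, by p times the covariate-by-drug effect, and power can rise or fall. With two additive covariates the reference point is model-based. At 50% each and independent, only 0.5 x 0.5 x 20 = 5 women are in that cell.

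**The case against.** The covariate effect needs three conditions together: present/absent coding, use in Aim 3, and crossing with drug. The plan states none of them. It refers to a cited study that may settle coding and scope and is not available here. If comorbidity is a score such as BDI-II, controls vary too and only medication is affected. All of this stands, and it makes the point conditional. But usual repeated measures ANCOVA does cross covariates with the within-subject factor, and nothing in the plan rules that out.

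On visit, no trend is documented, and the trial and reversal counts are exposure, not evidence of drift. The sentence in section 9 promising main effects for condition and group concerns the taste paradigm, so it should not be read as the term list for the drug model. The omission rests on the general silence of the analysis plan. These objections also stand.

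A reader might infer that omitting visit biases the drug effect or invalidates the tests. Randomised order prevents that. A reader might also infer that future sample sizes will be too large. That follows only if the later trial uses this residual SD and itself models visit. The plan does not say which SD is meant, and its one example is the SD for an AN-versus-control comparison.

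**Conclusion.** Both points hold in limited form, and the severity is minor.

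Omitting visit from a three-visit crossover costs precision, not validity. The cost is small for a weak trend (factor 1.06, a point or so of power) and material only for assumed trends of about 0.5/1.0 SD or more (factor 1.25 to 1.58, power about 0.72 to 0.62). This part bears on all three aims.

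The covariate wording leaves open an Aim 3 analysis whose estimate refers to AN at covariate zero, with power 0.72 instead of 0.80 in the 30%, one-covariate case. The documents do not support saying that the plan commits to that analysis. They also do not support saying that any use of these covariates alters Aim 3, since a main effect alone leaves group x drug unchanged. Aims 1 and 2 compare drug with placebo within AN, so this part does not reach them. Aim 3 is framed as pilot data, and the power section disclaims certainty.

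**What to change.** 1. Add visit (1/2/3) as a fixed effect in the drug and group x drug model, for example SPSS MIXED with a random subject intercept, and report the residual SD from that model. This uses 2 df and costs about 1 to 2 power points if there is no trend.
2. State how comorbidity and medication are coded and which tests take them.
3. Report the Aim 3 group x drug test without covariate x drug terms for comorbidity and medication. That contrast includes any effect of those factors on drug response. Use the terms, mean-centred, in AN-only sensitivity analyses to show how much they matter.
4. Label any covariate-crossed group comparison as controls versus AN at covariate zero.

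Making the uncrossed test the main one is partly a preference; clear labelling alone would remove the risk of misreading. All four are changes of plan wording and model specification and need no new data.
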